# 7.2 Treatment Regimens

The treatment group "as assigned" will be retrieved from the IRT system. The treatment group "as treated" is expected to be the same as the arm as assigned by IRT. However, if a participant received an incorrect treatment for the entire period of treatment, this will be documented as a relevant protocol deviation (see Section 8.2.3) and the participant's treatment group will be defined as the incorrect treatment the participant actually received.

# 7.2.1 Monotherapy Dose Escalation (Part 1)

In the monotherapy dose escalation part of the study, participants will receive BMS-986277 at one of the four planned dose levels (3 x  $10^{10}$ , 3 x  $10^{11}$ , 1 x  $10^{12}$ , or 3 x  $10^{12}$  vp). At each dose level BMS-986277 will be administered as a single IV infusion (D1) before proceeding to a single dosing cycle (3 doses, Days 15, 17, and 19). Participants who complete the first cycle without a

DLT, who have no clinical evidence of disease progression, and are considered suitable for further treatment may receive up to two more cycles of BMS-986277. Optional treatment up to 6 cycles if deemed safe and after risk/benefit evaluation and approval by Medical Monitor (or designee) are permitted.

# 7.2.2 Combination Dose Escalation (Part 2)

In the combination dose escalation part of the study, participants will receive combination treatment with nivolumab (480 mg Q4W up to 26 cycles) plus BMS-986277 at one of two dose levels (for up to 3 cycles). These two dose levels will be determined based on the results from the monotherapy dose escalation part. Participants who complete the first cycle and do not have a DLT, have not had disease progression, and are considered suitable for further treatment may receive up to two more cycles of BMS-986277 with each subsequent cycle beginning no sooner than 28 days after Day 1 of the previous cycle.

#### 7.2.3 Cohort Expansion (Part 3)

In the cohort expansion part of the study, participants will receive combination treatment with nivolumab (480 Q4W up to 26 cycles) in combination with BMS-986277 (at the RP2D based on Part 2 for up to 3 cycles). Participants who complete the first cycle and do not have a DLT, have not had disease progression, and are considered suitable for further treatment may receive up to 2 more cycles of BMS-986277, with each subsequent cycle beginning no sooner than 28 days after day 1 of the previous cycle.

# 7.3 Populations for Analyses

- All Enrolled: All participants who signed an informed consent form and are registered into the IRT
- All Treated: All participants who received at least one dose of any study medication
- Response-evaluable: All treated participants with measurable disease at baseline and one of the following: (a) at least one post-baseline tumor assessment, (b) clinical progression, or (c) death
- Pharmacokinetic: All treated participants who have evaluable concentration-time data
- Immunogenicity: All treated participants who have a baseline and at least one post baseline immunogenicity assessment
- Biomarker: All treated participants with evaluable biomarker data for the specific analysis
  - It is expected that all treated participants in Parts 2 and 3 are the same as the CD8 biomarker evaluable population.

#### 8 STATISTICAL ANALYSES

All analysis will be performed in SAS (Statistical Analysis System software, SAS Institute, North Carolina, USA) using version 9.2 or higher. Some figures may be generated using S-Plus.

#### 8.1 General Methods

Continuous variables will be summarized by using descriptive statistics, using the mean, standard deviation/standard error of the mean, median, minimum, and maximum values. Some continuous

variables may also be summarized using the geometric mean and coefficient of variation. Categorical variables will be summarized by frequencies and percentages of participants in the population falling into each category. Percentages given in these tables will be rounded and, therefore, may not always sum to 100%. Percentages less than 0.1 will be indicated as "< 0.1". If a missing category is not being presented in the data display, only those participants with non missing values for the parameter being assessed are included in the percentage calculation.

Statistical analyses will be presented by part, dose level, cohort, indication, and biomarker level; and any of the groups may be combined, where reasonable, to increase the number of participants for analyses. The grouping schemes for analyses are further described in the DPP.

Unless otherwise specified, listings will be sorted by part, dose level, cohort, and unique participant ID.

# 8.2 Study Conduct

#### 8.2.1 Accrual

The following will be presented on the All Enrolled population.

#### **Summary:**

• Number (%) of participants accrued by part, country and investigational site: Include country, site number, number of participants enrolled, and number of participants treated

#### Listing:

• Participants accrued by part, country and investigational site

#### 8.2.2 Protocol Deviations

A listing of deviations from the protocol inclusion and exclusion criteria for the All Enrolled population will be provided, along with the description of the criteria and whether they were treated. Participants who do not meet the inclusion and exclusion criteria and are subsequently treated are considered as protocol deviations. In the event that the inclusion and exclusion criteria are changed during the course of the trial, each participants' inclusion/exclusion criteria entered on the CRF will be linked to the criteria used at the time of their enrollment.

#### 8.2.3 Relevant Protocol Deviations

A relevant protocol deviation is a deviation from the protocol which is programmed in the database and which could potentially affect the interpretability of the study results. Non-programmable relevant eligibility and on-treatment protocol deviations, as well as significant (both programmable and non-programmable) will be reported through ClinSIGHT listings. The following programmable deviations will be considered as relevant protocol deviations and a listing based on the All Treated population will be provided. During the conduct of the trial, if any relevant protocol deviation is discovered that is not on this list, this SAP may be amended prior to the final database lock. Relevant protocol deviations, their implications, and subsequent data handling will be reported in the CSR.

#### **At Entrance:**

In the event that either of the following occur, the study team will consider whether the time relative to first dose is acceptable to be considered as the baseline assessment.

- Participants with a tumor tissue sample earlier than 35 days prior to first dose
- Participants whose baseline efficacy assessments are more than 28 days prior to first dose In the event that any of the following occur, the participants may be excluded from specific (or all) analyses upon study team agreement. Any exclusions due to relevant protocol deviations will be documented in the CSR.
- Participants in Parts 2 and 3 without an evaluable CD8 value prior to first dose.
- Participants without measurable disease at baseline (Inclusion Criteria 2.b).
- Participants in Parts 2 and 3 with a CD8 value  $\geq 20\%$  (Inclusion Criteria 2.f).
- Participants with screening ECOG performance status > 2 (Inclusion Criteria 2.g).
- Participants with prior exposure to checkpoint inhibitors or cytotoxic agents within 28 days prior to first dose (Inclusion Criteria 2.i and Exclusion Criteria 2.a).
- Participants with prior antiviral agents within 7 days prior to first dose or PEG-IFN within 14 days prior to first dose (Exclusion Criteria 2.e).

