### 10.3.1 Efficacy Analyses

The primary efficacy analyses (see Table below) will be performed on the treated population for the final analysis. Efficacy analyses based on the response-evaluable population may be performed for interim analyses when the minimum follow-up period is less than sufficient to warrant adequate interpretation of the result. Efficacy analyses will be performed using the RECIST v1.1 (all indications except prostate) or PCWG3 criteria (prostate), and may be repeated by BICR using iRECIST (all except prostate), if data permits. Details of the censoring scheme on time-to-event endpoints such as DOR (all except prostate), PFS, OS, immune DOR (iDOR), and immune PFS (iPFS) will be described in the Statistical Analysis Plan.

Endpoint	Statistical Analysis Methods
ORR is defined as the proportion of all treated participants whose BOR is either CR or PR. DCR includes CR, PR, and SD. BOR for a participant will be assessed per RECIST v1.1 or PCWG3 by BICR and/or by investigator, where available.	Estimate of ORR and DCR and corresponding 2-sided exact 95% CI using the Clopper-Pearson method
mDOR DOR for a participant with a BOR of CR or PR is defined as the time between the date of first response and the date of the first objectively documented tumor progression per RECIST v1.1/PCWG3 or death, whichever occurs first.	Estimate by the Kaplan-Meier method and corresponding 2-sided 95% CI using Brookmeyer and Crowley methodology (using log-log transformation)
mPFS and PFSR at 8, 16, and 24 weeks PFS for a participant is defined as the time from the first dosing date to the date of first objectively documented disease progression or death due to any cause, whichever occurs first	Estimate by the Kaplan-Meier method and corresponding 2-sided 95% CI using Brookmeyer and Crowley methodology (using log-log transformation) for the median and Greenwood formula for the rate
mOS and OSR at 3, 6, 9, and 12 months OS for a participant is defined as the time from the first dosing date to the date of death for any cause	Estimate by the Kaplan-Meier method and corresponding 2-sided 95% CI using Brookmeyer and Crowley methodology (using log-log transformation) for the median and Greenwood formula for the rate
Summary measures of indication-specific efficacy biomarkers, such as absolute PSA and PSA doubling time (prostate), CEA (colorectal), Ca125 (ovarian), and Ca19-9 (pancreatic)	Summary statistics/plots by visit Spider plots

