### 10.3.2 Safety Analyses

All safety analyses will be performed on the treated population.

Endpoint	Statistical Analysis Methods
Incidence of AEs, SAEs, AEs meeting protocol-defined DLT criteria, AEs leading to discontinuation, AEs resulting in death, and deaths AEs will be graded according to CTCAE v4.03	DLT rate by dose level; frequency distribution of treated participants with AE using the worst CTC grade. Participants will only be counted (1) once at the PT level, (2) once at the SOC level, and (3) once in the “total participant” row at their worst CTC grade, regardless of SOC or PT.
Incidence of clinical laboratory test abnormalities Laboratory values will be graded according to CTCAE v4.03	Laboratory shift table using the worst CTC grade on treatment per participant
Vital sign abnormalities or other safety biomarkers	Summary tables of vital signs Frequency statistics of renal function and bladder hemorrhage

Abbreviations: AE = adverse event; CTC = common terminology criteria; CTCAE = common terminology criteria for adverse events; DLT = dose-limiting toxicity; PT = preferred term; SAE = serious adverse event; SOC = system organ class

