# 3.3 Blinding and Unblinding

Not applicable. This is an open label study.

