# 8.5 Efficacy

Efficacy analyses will be based on the endpoints defined in Sections 5.2.1, 5.3.1, and 5.3.2.

The primary efficacy analyses will be performed on the All Treated population for the final analysis. Efficacy analyses based on Response-evaluable and/or CD8 Biomarker Evaluable populations may be performed as supportive analyses, particularly if these populations differ substantially from the All Treated population. If the majority of the All Treated population is included in Response-evaluable and/or CD8 Biomarker Evaluable populations, limited efficacy analyses may be performed on those populations (eg, ORR). For interim analyses when the minimum follow-up period is less than sufficient to warrant adequate interpretation of the result, efficacy analyses may be performed on Response-evaluable Participants.

Time to event distributions (eg, PFS, OS, and DOR) will be estimated using Kaplan-Meier (K-M) techniques. When appropriate, the median along with 95% confidence interval (CI) will be estimated using the Brookmeyer and Crowley methodology (using log-log transformation for constructing the CIs). Rates at fixed timepoints (eg, PFSR at 24 weeks or OSR at 12 months) will be derived from the K-M estimate and corresponding 95% CI will be derived based on the Greenwood formula using log-log transform^8. Confidence intervals for binomial proportions will be derived using the Clopper-Pearson method.

If BICR data is available, certain analyses (eg, ORR) may be repeated using the BICR data and presented by the accepted record after adjudication, Radiologist 1, and Radiologist 2. To assess concordance between BICR and investigator assessments, BOR may be cross-tabulated for the All Treated population for the assessment type (Investigator vs. BICR). Concordance will be assessed using the Gamma statistic and/or the Kappa coefficient. The concordance rate of responders will be computed as the frequency with which Investigator and BICR agree on the classification of a participant as a responder/non-responder. The concordance rate of progressors may be assessed similarly.

Indications for which the primary efficacy analysis is being performed using RECIST 1.1 may also be analyzed using iRECIST, if data is available. Analyses for iRECIST endpoints will use the same statistical methods as the analyses for RECIST 1.1 endpoints.

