# 8.6 Safety

Analysis of safety will be based on the All Treated population and presented by part, dose level, and overall; tabulations by cohort, indication, and biomarker level may also be performed, as appropriate. Deaths and SAEs will be listed using the All Enrolled population. The treatment groups will be "as treated" as defined in Section 7.2.

Adverse events will be coded according to the most current version of MedDRA at the time of each database lock and the severity will be graded using the NCI CTCAE version 4.03. Treatment-related AEs are those events with relationship to study treatment "Related" as recorded on the CRF. If the relationship to study treatment is missing, the AE will be considered as treatment related.

Listing of AEs will include all enrolled participants, as SAEs and deaths are collected pretreatment. Summaries of AEs will include (1) events occurring from the first dose date to 30 or 100 days (inclusive) after the last dose of either study treatment for Part 1 or Parts 2-3, respectively, for participants who are off study treatment and (2) all events occurring from first dose date for participants who are still on study medication.

Unless otherwise specified, the AE summary tables will be restricted to on-treatment events regardless of the causality. AEs and treatment-related AEs will be tabulated by descending frequency of system organ class (SOC) and descending frequency of preferred term (PT) within each SOC, unless otherwise specified. When reporting AEs by CTC grade, summary tables will be provided based on the event with the worst CTC grade (independent of relationship to study medication). Participants will only be counted (1) once at the PT level, (2) once at the SOC level, and (3) once in the 'Total participant' row at their worst CTC grade, regardless of SOC or PT.

The analysis of laboratory results will be based on the All Treated population with available data. Laboratory results will be categorized according to NCI CTCAE version 4.03 grade. Baseline is defined in Section 7.1.1. Summaries of laboratory results include baseline and (1) post-baseline results up to 100 days (inclusive) after the last dose of either study treatment for participants who are off study treatment and (2) all available post-baseline results for participants who are still on study medication.

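### SAP 8.2.3 lets the study team drop treated participants from any or all analyses, which contradicts the All Treated primary efficacy and safety analyses

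*SAP*

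**What the plan says.** SAP 8.2.3 (At Entrance) lists six deviations: no evaluable CD8 value before first dose (Parts 2 and 3); no measurable disease at baseline; CD8 of 20% or more (Parts 2 and 3); screening ECOG above 2; a checkpoint inhibitor or cytotoxic agent within 28 days; and a recent antiviral or PEG-IFN. For these, "the participants may be excluded from specific (or all) analyses upon study team agreement". The control placed on an exclusion itself is "Any exclusions due to relevant protocol deviations will be documented in the CSR".

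The analysis populations are stated elsewhere without exception:
- SAP 7.3 defines All Treated by receipt of at least one dose and makes no allowance for deviations.
- SAP 8.5: "The primary efficacy analyses will be performed on the All Treated population for the final analysis". Protocol 10.3.1 agrees that the primary efficacy analyses "will be performed on the treated population for the final analysis".
- SAP 8.6: "Analysis of safety will be based on the All Treated population". Protocol 10.3.2: "All safety analyses will be performed on the treated population".

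On blinding, SAP 3.3 reads "Not applicable. This is an open label study".

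**The concern.** The two sets of statements cannot both govern. If a dosed participant is removed from all analyses under 8.2.3, the tables headed All Treated no longer contain all treated participants. The choice is optional and made person by person, and the people making it can know each participant's adverse events and tumour response.

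Two results are exposed. The first is the primary endpoint, AE and DLT incidence: a dosed participant with a toxicity could be missing from the tables. The second is ORR in Cohorts 1 and 2. SAP 5.2.1 divides responders by the number in the population of interest, so each non-responder removed raises the estimate. Several of the listed deviations, such as poor performance status or recent cytotoxic therapy, could plausibly be related to outcome, so removal need not be neutral.

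**Working it through.** **Inputs.** SAP 6.3.1 and 6.3.2 (same figures in Protocol 10.1.2.1 and 10.1.2.2):
- Cohort 1: null rate 0.06, target 0.20, N = 35, X = 5, alpha 0.056, power 0.857; threshold rate 14.3%.
- Cohort 2: null rate 0.20, target 0.40, N = 33, X = 11, alpha 0.051, power 0.831; threshold rate 33%.
- The nominal one-sided alpha is 0.10 (SAP 6.3). The table footnotes define X as the smallest number of responders that shows the cohort is not futile.

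**Reproducing the plan.** With go defined as at least X responders and exact binomial tails:
- Cohort 1: P(R ≥ 5 | 35, 0.06) = 0.0563; P(R ≥ 5 | 35, 0.20) = 0.8565.
- Cohort 2: P(R ≥ 11 | 33, 0.20) = 0.0508; P(R ≥ 11 | 33, 0.40) = 0.8310.

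Both match. All ten cells of SAP Tables 4 and 5 reproduce to the printed three decimals.

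**Count reading.** Removing participants never adds responders. A cohort with 10 responders (or 4 in Cohort 1) stays below X whatever is removed, so no go can be created.

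**Rate reading, Cohort 2.** Start one response short, at 10/33 = 30.3%. After removing k non-responders the rate is 10/(33 − k), and it must reach 11/33 = 33.3%:
- k = 1: 10/32 = 31.3%
- k = 2: 10/31 = 32.3%
- k = 3: 10/30 = 33.3%, which meets the threshold

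The shift is 33.3 − 30.3 = 3.0 points, or 3/20 = 15% of the assumed 20-point difference. The Clopper-Pearson 95% interval moves from 15.6–48.7% to 17.3–52.8%.

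If three non-responders could always be removed, and no responder ever were, every trial with 10 or more responders would be a go: P(R ≥ 10 | 33, 0.20) = 0.107. If the three removals are unrelated to response, the chance is P(R ≥ 10 | 30, 0.20) = 0.061.

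**Re-derived X, Cohort 2.** If X were instead recalculated for the smaller N at nominal alpha 0.10, one removal would be enough: P(R ≥ 10 | 32, 0.20) = 0.090.

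**Rate reading, Cohort 1.** Start at 4/35 = 11.4%. Seven removals are needed: 4/28 = 14.3%. The worst case is P(R ≥ 4 | 35, 0.06) = 0.156. With removal unrelated to response it is P(R ≥ 4 | 28, 0.06) = 0.084. Seven of 35 is 20% of the cohort.

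**Safety.** SAP 8.6.1 tabulates DLTs on All Treated by dose level. As an illustration, take a dose level with six treated participants and two DLTs. Removing one participant who had a DLT changes the tabulated rate from 2/6 = 33% to 1/5 = 20%.

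**The case against.** The strongest reply is that the consequence is limited, and much of it stands.

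- A reader might infer that the clause can turn a no-go cohort into a go. The tables define X as a count, under which this is impossible. The flip needs the rate figures in the text to be taken as the rule, or X to be re-derived. The documents give both a count and a rate and do not say which applies when N changes.
- A reader might also take 10.7% and 15.6% as the actual error rates. They are ceilings. They assume enough non-responders with a listed deviation in every borderline trial, all of them removed and no responder removed. No expected deviation rate is given. Protocol 9 bars waivers and requires eligibility to be confirmed before assignment, and Protocol 7.2 replaces Part 3 participants whose CD8 level cannot be determined. Seven ineligible non-responders in Cohort 1 is unlikely.
- X appears only in the sample-size sections. The planned efficacy analysis is ORR with a confidence interval, and efficacy is a secondary objective.
- The direction of bias is not uniform. The assumed nivolumab response rates rise with CD8 (6%, then 20%). If that trend continued, excluding participants with CD8 of 20% or more would tend to lower ORR.
- Safeguards exist. The deviation list is prespecified and programmable, newly found deviations may be added by SAP amendment before final lock, and exclusions are reported in the CSR. AE listings cover all enrolled participants, and deaths and SAEs are listed on All Enrolled. A serious toxicity would therefore not vanish from the report.
- The clause is permissive, and nothing says it takes precedence over 8.5 and 8.6. Nor do the documents say it changes the DLT data entering the dose-escalation model.

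These points limit the size of the effect but do not remove the contradiction. The listings do not protect the incidence tables or ORR. CSR documentation discloses an exclusion without requiring the All Treated result to be shown. The pre-lock provision concerns the list, not the decision on an individual.

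**Conclusion.** Wrong as written: a stated rule contradicts the stated primary analysis populations, and no precedence is given. The defect is optional removal of dosed participants, with outcomes known, from AE and DLT incidence and from ORR. It does not depend on any go/no-go flip.

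On the count rule the effect on the go decision is nil. On a rate reading, Cohort 2 is the realistic case: three exclusions (9% of 33) move ORR by 3.0 points, and the false-go chance lies between 6.1% (removal unrelated to response) and 10.7% (only non-responders removed), against 5.1% by design. The upper figure just exceeds the nominal 10%. The Cohort 1 case, at most 15.6%, is arithmetically correct but unlikely. All these figures assume the design sizes of 33 and 35.

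A related defect is that the CD8 item lists 20% or more in Parts 2 and 3 as a deviation. The current Protocol (6.1, criteria 2e and 2f) accepts any CD8 level in Part 2 and enrols high-CD8 participants in Part 3 Cohort 3. SAP version 1.0 incorporates changes only up to Revised Protocol 03. Its 8.2.2 links entry criteria to those in force at enrolment, but 8.2.3 does not repeat this for the programmed list. Eligible participants could therefore become excludable.

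**What to change.** Replace the exclusion sentence in SAP 8.2.3 with:

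> Treated participants with these deviations remain in all All Treated safety and efficacy analyses; those without an evaluable CD8 value are counted in their assigned cohort and shown as CD8 unknown in biomarker-level tables. A supportive efficacy analysis may exclude every participant who meets a listed programmed criterion, applied uniformly, with the criteria fixed before database lock, and shown alongside the All Treated result.

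Align the CD8 item with the eligibility criteria in force when each participant enrolled.

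The cost is SAP wording and at most one additional supportive ORR table. No new data are needed, because the deviations are already programmed and SAP 8.5 already provides for supportive efficacy populations.
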